Patients who have undergone MRI perfusion imaging *without* referral for cardiac CTA will also be eligible for this study. For these patients, the coronary CT at rest will be performed as a research procedure followed by the stress portion of the CT perfusion study. No interpretation will be performed before the stress portion of the exam so all of these patients will receive the stress portion of the exam. These patients must have the clinically indicated MRI stress perfusion imaging as well as the research cardiac CTA with CT perfusion study completed within 60 days.

Patients who have undergone MRI stress perfusion imaging with a prior cardiac CTA will also be eligible for this study. These patients will only undergo the stress portion of CT perfusion study. These patients must have the clinically indicated cardiac CTA and SPECT as well as the research CT perfusion study completed within 60 days.

The CT perfusion scans will be analyzed and read by two highly trained CT readers (cardiologist and radiologist). In addition to assessing the safety and tolerability of the Lexiscan™ perfusion study, the CT perfusion findings will be compared diagnostically to SPECT and/or invasive catheter angiography if this is performed clinically after the research procedure.

Patient Flow Chart

Patients with heart rates > 65 bpm may receive beta-blockers in order to reduce their heart rate to values < 60 bpm. Patients with contraindications to the use of beta-blockers (chronic obstructive pulmonary disease, asthma sensitive to beta agonists, second- or third-degree heart block, hypotension as defined by systolic blood pressure <100 mmHg) are in principle eligible for participation in the study – however, no beta-blockers will be used in such individuals. Patients will receive nitroglycerin based on investigator judgment to better visualize the coronary arteries. Female subjects of childbearing potential will be given a urine pregnancy test prior to study enrollment. Pregnant persons will be excluded. Patients will receive a point-of-care serum creatinine test on the day of their research procedure before any contrast administration and patients with a serum creatinine greater than or equal to 1.5 mg/dL will be excluded from the study.

CT Coronary Angiography Protocol:

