Dynamic CT MPI data are reconstructed with a section thickness of 3 mm and a 2 mm increment with a medium smooth convoluted kernel (B30). The data are processed with the volume perfusion CT body application software and workstation (Siemens). After motion correction and 4D noise reduction, a double arterial input function is defined by placement of ROIs in the descending aorta in the cranial and caudal regions of the covered volume. After a volume of interest is manually defined around the left ventricle, the left ventricular myocardium is automatically segmented. A dedicated parametric deconvolution algorithm based on a two-compartment model of intravascular and extravascular space is used to derive myocardial blood flow and the volume transfer constant (k^{trans}) from the time-attenuation curves for each voxel.²³

Quantitative Measures of Myocardial Blood Flow from CT:

CT perfusion images will be analyzed on a dedicated console using commercially available software (Syngo Volume Perfusion™) as previously described.²⁴ Evidence of ischemia will be determined initially by visual comparison of rest and stress CT perfusion scans. Perfusion defects will be visually rated as reversible (only present at stress), fixed (present at both rest and stress) and mixed (more pronounced at stress, partly reversible at rest). Quantitative analysis of myocardial perfusion will be performed and mean blood volume (MBV), mean blood flow (MBF), and mean transit time (MTT) of each myocardial segment will be recorded. Readers will be blinded to the results of SPECT or invasive angiography examinations. The values obtained will be compared to historical published values for each parameter (MBF, MBV, and MTT) obtained using older generation CT perfusion protocols, MRI perfusion, or dynamic perfusion scanning.

Analysis of SPECT images:

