SPECT will be used as a comparator for the CT perfusion images. SPECT examinations will be interpreted for perfusion defects by two experienced readers (one nuclear medicine physician and one cardiologist). Images will be analyzed on a dedicated console using commercially available software. Evidence of ischemia will be determined by visual comparison of rest and stress SPECT perfusion scans as well as quantitative analysis available through the commercial analysis program. Perfusion defects will be visually rated as reversible, fixed, or mixed. Readers will be blinded to the results of CT perfusion data and invasive coronary angiography examinations.

Analysis of MRI stress perfusion images:

MRI stress perfusion imaging will be used as a comparator for the CT perfusion images. MRI examinations will be interpreted for perfusion defects by two experienced readers (one radiologist and one cardiologist). Images will be analyzed on a dedicated console using commercially available software. Evidence of ischemia will be determined by visual comparison of rest and stress MRI perfusion scans as well as quantitative analysis available through the commercial analysis program. Perfusion defects will be visually rated as reversible, fixed, or mixed. Readers will be blinded to the results of CT perfusion data and invasive coronary angiography examinations.

Image Quality:

Subjective assessment of image quality, coronary artery visualization, and perfusion images will be performed by two independent observers using a semiquantitative rating scale of 0 – 5. Image quality will be graded on a five-point scoring system: 1 non-diagnostic; 2 limited diagnostic value; 3 adequate (presence of artifacts not limiting detection of luminal stenosis); 4 good; 5 excellent.

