We will present comparisons of normal or abnormal perfusion determined from SPECT/MRI stress perfusion imaging or CT perfusion using the standard 17-segment model. We will also present a comparison of ischemia by CT perfusion (based on vascular territory) compared to anatomic evidence of significant CAD at catheterization. Any segments cut off by the limited z-axis scan range on perfusion CT will be excluded. Given 30 patients, we will have a maximum of 510 regions available to compare CT perfusion and SPECT/MRI stress perfusion. We will first perform a binary analysis where each segment is classified as either normal or abnormal, since the relative severity of perfusion defects has not been defined for CT. If feasible based on the number of patients with SPECT/MRI stress perfusion scans, we will compare the number of abnormal segments in each patient by each methodology using a kappa statistic. We will also use standard SPECT/MRI stress perfusion grading of perfusion (1 – 4 scale) and a similar scale for CT perfusion defect severity (also 1 – 4) based on prior measurements of absolute myocardial perfusion (ml/100 ml/min) with each segment graded as 1, 2, 3 or > 4 standard deviations from the norm. We will then perform linear regression (Pearson's correlation) to derive R values for CT perfusion versus SPECT/MRI stress perfusion imaging perfusion grade for each segment.

E. PROTECTION OF HUMAN SUBJECTS

E.1 RISK TO THE SUBJECTS

E.1.a Human Subject Involvement and Characteristics

This study will include 100 adults who present to the MUSC ED, hospital, or outpatient clinic with a clinical history and symptoms suspicious for cardiac ischemia and who have undergone or will likely undergo nuclear stress testing (SPECT).

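### The CT perfusion reading rule masks SPECT and invasive angiography but omits MRI, a comparator already completed when MRI-route patients have their research CT

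*Combined protocol and SAP*

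**What the plan says.** Section D.1 contains three masking rules for perfusion reads.

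- CT perfusion (under Quantitative Measures of Myocardial Blood Flow from CT): "Readers will be blinded to the results of SPECT or invasive angiography examinations".
- SPECT and MRI (under their own analysis subsections, in identical words): "Readers will be blinded to the results of CT perfusion data and invasive coronary angiography examinations".

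MRI has the same role as SPECT: "MRI stress perfusion imaging will be used as a comparator for the CT perfusion images". The CT read starts as a visual judgement: "Evidence of ischemia will be determined initially by visual comparison of rest and stress CT perfusion scans".

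MRI patients can enter with or without an earlier CTA. For the former, D.1 says: "Patients who have undergone MRI stress perfusion imaging with a prior cardiac CTA will also be eligible for this study".

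Section D.2 then uses the reads: "We will present comparisons of normal or abnormal perfusion determined from SPECT/MRI stress perfusion imaging or CT perfusion", by segment in the 17-segment model. It adds a kappa on the per-patient count of abnormal segments if numbers allow, and a per-segment correlation of severity grades.

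**The concern.** The masking rules work by naming tests. A test that is compared but not named is not protected. MRI is compared with CT perfusion but missing from the CT readers' list. Coronary CTA is missing from the SPECT and MRI readers' lists.

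These are visual ratings, and D.2 begins with a normal/abnormal call per segment because defect severity is not yet defined for CT. A borderline segment is the one most easily settled by knowing what the other test showed. That would make CT and MRI agree more often than the images alone support.

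Sections A and D.2 say the comparative data are meant to help plan later, adequately powered accuracy studies. Inflated agreement would carry into that planning, and no later analysis can remove it from reads already made.

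**Working it through.** The plan states no figure on this point, so the check compares the masking rules with the comparisons planned and with the order of examinations.

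**Step 1. What each reader is masked to (D.1).**

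| Read | Masked by name | Relevant result not named |
|---|---|---|
| CT perfusion | SPECT, invasive angiography | MRI stress perfusion |
| SPECT | CT perfusion, invasive angiography | coronary CTA |
| MRI | CT perfusion, invasive angiography | coronary CTA |

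The word 'invasive' prevents reading the angiography entry as covering CTA. The only other masking statement, under Image Quality, hides acquisition parameters from the observer making measurements. It fills neither gap.

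**Step 2. Which direct comparisons are open.**
- CT against SPECT: CT readers are masked to SPECT, and SPECT readers to CT perfusion. Closed both ways.
- CT against MRI: MRI readers are masked to CT perfusion, but CT readers are not masked to MRI. Open one way.

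**Step 3. Whether the unmasked result exists at the time of the read.**

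| Route (D.1) | MRI known at the CT read? | CTA known at the SPECT or MRI read? |
|---|---|---|
| Referred for CTA | No MRI foreseen | Possible if SPECT follows the CTA |
| SPECT, no CTA referral | No MRI foreseen | Not if read before the research CTA |
| SPECT, prior CTA | No MRI foreseen | Possible |
| MRI, no CTA referral | Possible: MRI is done first | Not if read before the research CTA |
| MRI, prior CTA | Possible: MRI is done first | Possible |

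In both MRI routes the patient must already have undergone MRI, as inclusion criterion 2 in E.1.a also says. The CT readers and the MRI readers are each one cardiologist and one radiologist, and nothing requires them to be different people.

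**Step 4. Which analyses are exposed (D.2).** The normal/abnormal calls, and any kappa built on them, depend most on the reader. The CT severity grade used in the correlation is different. It comes from absolute perfusion in standard deviations from normal, produced by software after a manually drawn volume, so reader knowledge has less room to move it.

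**Step 5. Extent.** D.2 works with 30 patients and 30 × 17 = 510 segments for SPECT and MRI together. If m of the 30 are MRI patients, the direct gap touches at most 17m of the 510 segments. The plan does not give m, so the exposed share m/30 could lie anywhere from 0 to 1. This measures exposure only. The bias itself would also need the expected agreement and the effect of knowing the MRI, and the documents give neither.

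**The case against.** The best reply is that this is incomplete drafting with little consequence. There are signs that MRI was added to a SPECT protocol without every sentence being updated: the window for MRI patients with a prior CTA still asks for SPECT, and D.1's sentence on diagnostic comparison leaves MRI out. The plan is silent and does not say that readers will see the MRI. This is fair, but staff will apply the list as written, and intent does not mask a report already on file.

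The objection has more force on coronary CTA. The rest CT serves as part of the rest/stress CT examination, so masking to CT perfusion data may partly cover those images, though not clearly a stenosis report. A SPECT or MRI read made before a research-only CTA cannot be affected. The CTA does not always come before SPECT in the referral route, since D.1 also admits patients who have already had SPECT. If clinical reads serve as study reads, masking CTA could require re-reading. This half is therefore a secondary point.

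Three stronger readings are tempting, and the documents do not support them.

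- A reader might infer that the whole modality comparison is open to review bias. It is not: CT perfusion and SPECT are masked from each other in both directions.
- A reader might try to size the effect with a two-by-two table and a rise in kappa. The counts would be invented, all 30 patients would be treated as unmasked, and a per-patient normal/abnormal table is not the kappa that D.2 plans.
- A reader might conclude that the trial's main findings are at risk. Section A rules out a preplanned accuracy comparison with SPECT or MRI, and D.2 says the study is not powered for accuracy.

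**Conclusion.** The MRI omission stands. As written, the CT perfusion read may be made with the MRI result known, and this can inflate CT-versus-MRI agreement in MRI-route patients. The CTA omission from the SPECT and MRI lists is real but weaker, and matters only where a CTA precedes the read.

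The direction of the MRI bias is towards too much agreement, assuming that a reader who knows the MRI tends to move towards it. Its size cannot be calculated from the documents. It is limited to the secondary descriptive comparison: mainly the visual normal/abnormal calls, less the quantitatively derived CT grades. The primary safety, tolerability and feasibility aims are unaffected. The wording should be corrected before study reads are made, but the gap does not threaten the trial's main purpose.

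**What to change.** 1. **D.1, Quantitative Measures of Myocardial Blood Flow from CT.** Add MRI stress perfusion to the masked results, for example: *CT perfusion readers will have no access to SPECT, MRI stress perfusion or invasive angiography results.* This costs one phrase. CT readers keep the rest images they need for the rest/stress comparison.
2. **D.1, Analysis of SPECT images and Analysis of MRI stress perfusion images.** Add coronary CTA results to both lists where study reads are made separately from clinical reads. State which kind of read is used and when it is made. This is a wording change if separate study reads are planned. If clinical reads are used, masking CTA would mean re-reading, and the investigators may reasonably choose to report the limitation instead.
3. **Readers.** State whether the same cardiologist or radiologist may read both CT and MRI for one patient and, if so, how the sessions are kept apart.

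If reads have already been made under the present wording, report CT against MRI separately from CT against SPECT, and state which results the CT readers had seen.

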Studies will be performed using a 3rd generation, dual source CT scanner capable of coronary imaging at < 1mSv (Siemens, SOMATOM™ Force). The coronary CTA will be performed based on standard clinical indications that conform to published appropriate use criteria. The scan will be done using our usual clinical protocol with administration of 30 – 60 cc of an intravenous contrast agent (Ultravist 370). Acquisition mode (axial, prospective, retrospective or flash) is chosen based on heart rate, rhythm and body size. We will accept patients who have the SPECT study done within 30 days of the scheduled CTA and/or research scan(s).

Pharmaceutical Stress Protocol:

Pharmacological stress testing will be performed with a single injection of 0.4 mg of regadenoson (Lexiscan™) under physician and nursing supervision per MUSC clinical protocol. The cardiologist responsible for clinical stress administration will review a pre-Lexiscan™ EKG and patient medical history to ensure Lexiscan™ can be administered safely. A post-Lexiscan™ EKG will be obtained and read and the cardiologist will determine if and when the patient can be discharged safely.

Analysis of CT Coronary Angiography Images:

CT coronary angiograms will be evaluated by consensus of two experienced investigators. Images will be analyzed using both axial source images and by analyzing dedicated 2D and 3D visualization techniques such as Maximum Intensity Projection (MIP), curved Multiplanar Reconstruction (MPR) and 3D Volume Rendering (VRT).

CT myocardial perfusion protocols:

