All measurements and calculations will be performed by one observer who will be blinded to image acquisition parameters. We will also measure the signal-to-noise ratio (SNR) and contrast-to-noise ratio (CNR) for the coronary CTA and the perfusion images. Circular regions of interest will be placed in the aortic root at the level of the left main coronary artery ostium (size 100 mm²) as well as in the proximal segments of the left and right coronary arteries and the left lateral ventricular wall (size 1 – 4mm²). Signal intensity (CT number in HU) and noise (HU standard deviation) will be recorded in each region. All regions-of-interest will be measured three times and mean measurements will be used for statistical analysis. The SNR will be calculated as the mean HU divided by the mean image noise measured in the aorta. The CNR will be calculated by subtracting the mean HU in the left lateral ventricular wall from the mean HU within the lumen of the proximal coronary arteries and dividing this difference by the image noise measured in the aorta.²⁶ These values (SNR and CNR), although standard measures of image quality in CT research, cannot be compared directly between CT and SPECT. However, they can be used as a quantitative gauge to compare image quality between the 3rd generation CT scanner with low radiation imaging and the older CT perfusion scans that required higher radiation exposure.

Analysis of radiation dose:

The CT dose index and dose-length product will be recorded by the scanner and collected for each image acquisition. Effective radiation dose will be calculated by using a standard conversion factor of 0.0145 for adult chest CT²⁷. For SPECT examinations, the effective radiation dose will be estimated by multiplying the administered activity of ^{99m}Tc-tetrofosmin with a tracer-specific conversion factor of 0.008 for rest and 0.0069 for stress acquisition. The effective radiation doses of rest and stress SPECT acquisition will then be combined to compute the net radiation dose²⁸. The radiation dose of the CT myocardial perfusion will be compared with the radiation dose obtained with the previous (older) scanner at our institution in order to have a direct comparison of the radiation exposure decrease to the patient. Patients who have MRI stress perfusion imaging as the comparative imaging study will be excluded from the radiation dose analysis.

Safety and Tolerability Assessment:

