This study is intended to primarily demonstrate feasibility, safety, and tolerability of Lexiscan™ for use as a coronary vasodilator during perfusion CT imaging. The study is not powered to prove the diagnostic accuracy of perfusion CT imaging with low radiation compared to SPECT or the current gold standard approach of invasive coronary angiography with invasive fractional flow reserve (FFR) measurement. Nonetheless, we will use the available comparative data for each technique (SPECT, MRI stress perfusion imaging, and invasive angiography) to help design subsequent clinical trials that are adequately powered for an accuracy endpoint. We anticipate that about 15 out of the 30 participants who undergo the CT perfusion portion of the study will have available cath comparisons.

Continuous data are displayed as mean ± SD, if normally distributed, or median and interquartile range if not normally distributed. Binary data are are displayed as proportions. Data will be reported as means ± SD or rates with 95 percent confidence intervals. A difference with P value of 0.05 or less will be considered significant.

Subjective image quality scores will be compared using the Chi-squared test with the Yates continuity correction for categorical variables and inter-observer agreement for image quality will be calculated using Cohen kappa (K) statistics and interpreted as follows: ≤ 0.20 slight or poor agreement, 0.20 – 0.40 fair agreement, 0.40 – 0.80 moderate agreement, ≥ 0.80 excellent agreement. For each group, comparisons of patient characteristics will be performed using the Chi-squared test for categorical variables and t-test or Mann-Whitney-U-test for continuous variables as appropriate.

Quantitative data (CNR, radiation dose) will be tested using a non-parametric significance test.

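### The CT perfusion dose comparison with the previous scanner is called direct, but it is in effect historical, its comparator cohort is undefined, and no adjustment or matching is planned

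*Combined protocol and SAP*

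**What the plan says.** Under Analysis of radiation dose (D.1), the CT perfusion dose "will be compared with the radiation dose obtained with the previous (older) scanner at our institution", and the stated purpose is "in order to have a direct comparison of the radiation exposure decrease to the patient". Under Image Quality (D.1), SNR and CNR are also to be set against scans from the earlier system, in softer terms: "they can be used as a quantitative gauge to compare image quality between the 3rd generation CT scanner with low radiation imaging". The comparator in that sentence is described as "the older CT perfusion scans that required higher radiation exposure".

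The analysis is in D.2: "Quantitative data (CNR, radiation dose) will be tested using a non-parametric significance test", with the general rule "A difference with P value of 0.05 or less will be considered significant". D.2 names no covariate, matching or stratification for dose or CNR. It adds "For each group, comparisons of patient characteristics will be performed using the Chi-squared test for categorical variables", but does not define the groups.

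On acquisition, D.1 treats the two scans separately:

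- Coronary CTA: "Acquisition mode (axial, prospective, retrospective or flash) is chosen based on heart rate, rhythm and body size".
- CT perfusion: one ECG-triggered shuttle mode for everyone, 30 seconds, 300 mAs per rotation, 80 to 100 kV, and 14 or 15 volumes. The basis for choosing the kV is not given.

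Section C reports vendor estimates of a dose reduction above 20% for routine scans and up to 50% for cardiac scans, including perfusion. Section B makes high radiation exposure one of the two issues that the study sets out to address.

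**The concern.** The word direct suggests that the two doses differ only because of the scanner. Nothing in the plan has the same patient scanned on both systems or allocates patients between them. The Facilities section places the perfusion scans on the new scanner only. The older doses therefore come from other patients, and, although the text implies this rather than states it, from an earlier period.

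If the two cohorts differ in body size or heart rate, an unadjusted test credits that difference to the scanner or sets it against the scanner. The older cohort is also undefined, so a reader cannot judge how far it resembles the study patients, and the analyst is free to choose it after the study doses are known. At stake is a published dose reduction that answers one of the two stated study goals and could be partly case mix. The SNR and CNR comparison has the same weakness.

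**Working it through.** **No figure to reproduce.** The documents give no sample size, SD, expected ratio or older-cohort number for this comparison. What follows illustrates the possible size of the problem under stated assumptions and is not an estimate of actual bias.

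**Inputs from the documents.** 80 to 100 kV, 300 mAs per rotation, 14 or 15 volumes (D.1, CT myocardial perfusion protocols); 30 patients with CT perfusion and significance at 0.05 (D.2); reductions above 20% and up to 50% (section C).

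**Assumptions.** At equal mAs, dose is proportional to kV^b with b = 2 to 3. The shares scanned at 100 kV, the log-dose SD (0.2 to 0.4), the older-cohort size and the two-sided test are also assumed.

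**Step 1: the kV range alone.** Reduction = 1 − (80/100)^b.
- b = 2: 1 − 0.640 = 36%.
- b = 3: 1 − 0.512 = 49%.

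**Step 2: a different kV mix with no scanner benefit.** This assumes that kV follows patient size on both scanners. With share p at 100 kV and r = (80/100)^b, mean relative dose is p + (1 − p)r.
- New 30%, old 70%: b = 2 gives 0.748/0.892, an apparent reduction of 16%; b = 3 gives 0.658/0.854, 23%.
- New 50%, old 70%: b = 2 gives 0.820/0.892, 8%; b = 3 gives 0.756/0.854, 11%.
- The bias can also run the other way. With new 70% and old 30% at b = 2, the factor is 0.892/0.748 = 1.19, and a true 20% reduction would appear as 1 − 0.80 × 1.19 = about 5%.

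**Step 3: number of volumes.** 1 − 14/15 = 6.7%.

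**Step 4: what the test does with a case-mix shift.** Two-sided Mann-Whitney test at 0.05, no true scanner effect, 4,000 simulated trials per setting. Ranges run from log-dose SD 0.4 to 0.2.

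| Per group | Shift in dose | Significant |
|---|---|---|
| 30 | none | 4% to 5% |
| 30 | 10% | 16% to 49% |
| 30 | 20% | 54% to 99% |
| 100 | 10% | 45% to 95% |

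A larger older cohort does not help: with more patients, the same shift is declared significant more often.

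**Step 5: CNR.** Section E.3 notes that iodine attenuates more at low photon energies, so kV affects contrast as well as dose. For the coronary CTA images, the acquisition-mode sentence adds a documented dependence on body size, rhythm and heart rate.

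**The case against.** The strongest case against is that the protocol nowhere says that perfusion dose depends on body size or heart rate. The sentence on acquisition mode stands under the coronary CTA protocol, whereas the comparison called direct is of perfusion dose, where mode and mAs are the same for all. This stands. A reader might infer that the protocol itself names the confounders of perfusion dose, but it does so only for the CTA images. For perfusion, the documented variation is in kV and number of volumes, and a link to size or heart rate is plausible only.

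A reader might also infer that the main hypothesis is at risk. It is not: section A sets lower dose against conventional nuclear imaging, and D.2 describes the study as primarily one of feasibility, safety and tolerability. Nor is the CNR comparison called direct, and the section C reductions are vendor expectations, not results of this study.

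Two further objections stand in part. The D.2 test is unnamed and not tied to this comparison; since SPECT dose is also collected, it may be meant for that contrast too. But no other method is offered for the older-scanner contrast. And comparing patient characteristics by group might reveal an imbalance, if the older cohort is one of the groups, but it would not correct one.

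**Conclusion.** The point holds in a limited form. The older-scanner comparison of perfusion dose is between different patients, has an undefined comparator and no planned adjustment, so direct overstates it. The SNR and CNR comparison is likewise unadjusted.

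The possible size is material against what the study hopes to see: 8% to 23% from the assumed differences in kV mix, and 36% to 49% across the whole kV range, beside vendor figures of more than 20% and up to 50%. These figures rest on the assumed kV exponent, on assumed shares, and on kV being chosen partly by patient size. Where lower kV is possible because of the new scanner, that part is a true benefit and not bias.

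The documents do not support concluding that an observed reduction would be spurious, or that the cohorts do differ. This is an inexpensive improvement to a supporting comparison and does not threaten the main hypothesis.

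**What to change.** 1. Drop the word direct, and describe the comparison as historical.
2. Define the older cohort before analysis: dates, scan protocol, selection rule and number. State also which study patients enter. D.1 removes those with MRI as comparator from the dose analysis, although their CT dose is usable in a CT-versus-CT comparison.
3. Extract body size, heart rate, kV and number of volumes for both cohorts.
4. Report the new-to-old ratio of CTDIvol and DLP on the log scale with a 95% CI, adjusted for or matched on body size and heart rate. Effective dose is DLP times a fixed 0.0145, so its ratio equals the DLP ratio if the same factor is applied to both cohorts.
5. Report kV and volumes by cohort, but do not adjust for kV where lower kV is part of the scanner's benefit.
6. Treat CNR in the same way, adding rhythm for the coronary CTA images.
7. Name the non-parametric test and keep it as the unadjusted, descriptive result.

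The cost is data extraction for the older scans, one regression or matching step, and a slightly wider interval; no patients or procedures are added. It assumes that the older records or images can be retrieved, which the documents do not say. If size data cannot be obtained, label the comparison descriptive and historical and draw no conclusion about the scanner's own effect.
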